14.2 On-Site Audits and Inspections

Domestic and foreign regulatory authorities, the EC or IRB, and an auditor authorised by the Sponsor may request access to all source documents, eCRFs, and other study documentation for on-site audit or inspection. Direct access to these documents must be guaranteed by the investigator, who must provide support at all times for these activities. Medical records and other study documents may be copied during audit or inspection provided that patient names are removed on the copies to ensure confidentiality.

In case the study site is patient to an inspection by regulatory bodies, the investigator will inform the sponsor promptly after the notification of such inspection.

15 STATISTICAL CONSIDERATIONS

The analysis of study data will be detailed in a separate statistical analysis plan (SAP). Some of the analyses may be reported separately as specified in the SAP.

15.1 Statistical Methods

15.1.1 General Considerations

The analysis will be computed with SAS Version 9.4 (Copyright© 2013 by SAS Institute Inc., Cary, NC, USA).

Unless otherwise specified, baseline is defined as the last planned assessment prior to first dosing and no subgroup analysis is currently planned.

Missing safety, pharmacodynamic, pharmacokinetic and clinical data will not be replaced and will be treated as missing from summary and statistical analyses.

Unless otherwise specified, all treatment comparisons will be two-sided and significance will be assessed at the 5% level.

All safety, pharmacokinetic, pharmacodynamic and clinical data will be summarised by treatment group (Placebo, Dose level 1, Dose level 2 and Dose level 3), and visit, as appropriate.

Qualitative variables will be presented using the number of patients, the number of missing values, the frequency and the percentage per modality.

Quantitative variables will be reported using the number of patients, the number of missing values, the mean, the standard deviation, the median, the first and the third quartiles, the minimum and the maximum.

Between groups comparisons are calculated using an independent t-test or ANOVA-test for quantitative variables with a parametric distribution, or Mann-Whitney test or Kruskal Wallis-test for variables with a non-parametric distribution.

Data is tested for normality using Kolmogorov-Smirnov-test.

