8.2 Adaptive Design

This study incorporates the use of an adaptive design. Study specific adaptive features and their limits are described in Table 3.

Table 3: Adaptive Protocol Features.

Adaptive study design areas	Features	Limits
Repetition of cohorts	
 Cohorts in stage 1 can be repeated in order to obtain more safety and PK data 	
 Each cohort in stage 1 can be repeated only once The randomisation will follow the originally planned system
Dose levels	
 Dose levels in stage 2 of the study can be dropped or adjusted in accordance with PK, safety and tolerability data collected up to the decision-making point 	
 The maximum dose will not exceed 5.0 mg/kg for the loading dose and 3.0 mg/kg/h for the maintenance dose If a dose level is dropped, the planned number of patients may be reassigned to the remaining dose levels.
Samples and assessments	
 Timing of PK and/or biomarker samples may be adjusted in accordance with evolving data and dosing schedule. Additional or less PK and/or biomarker samples may be taken in accordance with evolving data and dosing schedule. Biomarker measurements may be added or removed in accordance with evolving data and dosing schedule (e.g. mTREM-1) 	
 Minimum: sufficient PK samples according to the respective study objective Study specific maximum blood volume will not be exceeded (see section 12.12.8).
Time Window between onset of shock and initiation of treatment	
 The time window of 24 hours between onset of shock and start of study drug infusion may be shortened for stage 2 in accordance with evolving feasibility data from stage 1 	
 The allowed time window in stage 2 will not be shorter than 12 hours

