9 SELECTION OF PATIENTS

9.1 Number and Source of Patients

A total of 48 patients is planned. There will be 12 patients in stage 1 (4 per dose level) and 36 patients in stage 2 (9 per dose level). No formal sample size calculation was performed. The number of patients was chosen on the basis of similar studies investigating the safety, tolerability and pharmacokinetics of a drug product. In stage 1, the patients will be treated in three sequential cohorts with ascending dose levels of 4 patients each. Stage 2 of the study has a parallel-group design, where three dose levels of MOTREM will be compared to placebo.

Patients admitted to the participating intensive care units (ICUs) for septic shock will be screened at admission for eligibility. The eligibility criteria are identical between the two stages of the study.

The maximum number of patients according to the adaptive features of the study protocol will not exceed 66 patients, as specified below:

- Each cohort in stage 1 can be repeated once for the collection of additional safety data
- In each cohort in stage 1, one patient not completing 24 hours of study drug infusion will be replaced

At sites, who are conducting more than one clinical trial competing for the same patient population, a selection bias should be avoided. Random allocation of patients with the diagnosis to the different trials is an acceptable method for the minimisation of such bias and is recommended (19). A respective procedure should be in place at these sites.

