15.2 Determination of Sample Size

A formal sample size calculation was not performed for the primary objective of the study. Instead, the sample size 48 patients overall (N=12 for each dose level) was chosen to provide sufficient data for this pilot study of MOTREM in patients with septic shock. This is in line with recommendations for sample size of pilot studies (23).

As this is an exploratory study no adjustments for multiplicity will be employed.

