15.3 Randomisation Methods

The randomisation lists will be performed by Ascopharm Statistician using SAS software Version 9.4 (Copyright© 2013 by SAS Institute Inc., Cary, NC, USA) with the procedure “PROC PLAN” before the start of the study.

Randomisation lists produced will be implemented into the randomisation module of the Ennov Clinical© software (V7.5 or higher).

The first randomisation list for the stage 1 will be created with a minimum of 3 randomisation blocs of 4 i.e. 12 patients. Each sequential cohort (0.3, 1.0 and 3.0 mg/kg/h of MOTREM) will contain 4 patients (3 active and 1 placebo). Patient satisfying eligibility criteria will be randomised in a 3:1 ratio per cohort to the treatments as specified below:

- MOTREM
- Placebo

The second randomisation list for the stage 2 will be created with a minimum of 9 randomisation blocs of 4 i.e. 36 patients. Each dose group will contain 9 patients. Patient satisfying eligibility criteria will be randomised in a 1:1 ratio to the treatments as specified below:

- Dose level 1
- Dose level 2
- Dose level 3
- Placebo

For security, the two randomisation lists will be extended over the number of patients initially planned. For example, for the stage 1, three extra cohorts of 4 patients each will be planned as cohorts could be repeated once.

A randomisation list will be provided to the site’s pharmacy, who is in charge of blinding and labelling of the treatments.

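### The analysis groups combine Stage 1 and Stage 2 with no stage term and no rule for a dropped or adjusted dose, so those two adaptations would distort the dose results

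*Combined protocol and SAP*

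**What the plan says.** Section 15.1.1 fixes the reporting groups: "All safety, pharmacokinetic, pharmacodynamic and clinical data will be summarised by treatment group (Placebo, Dose level 1, Dose level 2 and Dose level 3". It names t-test or ANOVA, or Mann-Whitney or Kruskal-Wallis, for between-group comparisons, and plans no subgroup analysis. Section 15.1.5 adds an ANOVA on logs for PD endpoints, with each dose contrasted with placebo at the two-sided 10% level. Stage appears in none of these.

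Section 15.2 gives the size: "the sample size 48 patients overall (N=12 for each dose level) was chosen to provide sufficient data for this pilot study". Section 15.3 uses two randomisation lists. For Stage 1, "Each sequential cohort (0.3, 1.0 and 3.0 mg/kg/h of MOTREM) will contain 4 patients (3 active and 1 placebo". The Stage 2 list "will be created with a minimum of 9 randomisation blocs of 4 i.e. 36 patients. Each dose group will contain 9 patients".

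Table 3 in section 8.2 sets the permitted adaptations. "Dose levels in stage 2 of the study can be dropped or adjusted", and patients freed by a dropped dose may be reassigned. Each Stage 1 cohort may be repeated once. The 24-hour window from shock onset to treatment "may be shortened for stage 2 in accordance with evolving feasibility data from stage 1", to no less than 12 hours. No passage says how a patient on an adjusted dose is labelled or how a dropped dose is compared.

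**The concern.** The stages are randomised from separate lists and run one after the other, and Stage 1 patients were never randomised between doses. If arms differ in their Stage 1 share, a difference between stages is read as a dose effect. The synopsis lets only doses judged safe and well tolerated enter Stage 2, so a dropped dose may be the one with a safety signal, and safety is the primary objective. Separately, dose/PD is a secondary objective and PK is summarised by treatment. Both need each label to mean one dose.

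**Working it through.** **Reproducing the plan's counts.** Stage 1: 3 × (3 + 1) = 12. Stage 2: 4 × 9 = 36. Total: 48. Each dose: 3 + 9 = 12. Placebo: 3 × 1 + 9 = 12. The stated 12 per level therefore requires both stages. The ceiling in section 9.1 also reproduces: 48 + 12 (three repeated cohorts) + 6 (one replacement in each of up to six cohorts) = 66.

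**Formula.** Let d be an additive difference between stages in SD units. The bias in an unadjusted dose-placebo difference is d × g, where g is the Stage 1 share of the dose arm minus that of placebo. The documents give no value for d. I assume 0.5 and 1.0.

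| Scenario | Placebo share | Dose share | g |
|---|---|---|---|
| No adaptation, or window shortened alone | 3/12 = 0.25 | 3/12 = 0.25 | 0 |
| All cohorts repeated | 6/15 = 0.40 | 6/15 = 0.40 | 0 |
| One cohort repeated: that dose | 4/13 = 0.31 | 6/15 = 0.40 | +0.09 |
| One cohort repeated: other doses | 4/13 = 0.31 | 3/12 = 0.25 | -0.06 |
| Dropped dose, placebo not enlarged | 3/12 = 0.25 | 3/3 = 1.00 | +0.75 |
| Dropped dose, 3 of the 9 freed patients to placebo | 3/15 = 0.20 | 3/3 = 1.00 | +0.80 |
| Cohort repeated, then that dose dropped | 4/13 = 0.31 | 6/6 = 1.00 | +0.69 |
| Retained doses, one dose dropped, 9 freed patients to doses only (5 and 4) | 3/12 = 0.25 | 3/17 = 0.18 and 3/16 = 0.19 | -0.07 and -0.06 |
| Retained dose, two doses dropped, all 18 freed patients to it | 3/12 = 0.25 | 3/30 = 0.10 | -0.15 |

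**False-positive rates.** These come from 20,000 simulated four-group ANOVAs per scenario, using the nominal 10% contrast without a stage term.

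- No adaptation: about 9% (d = 0.5) and 7% (d = 1.0). The test is conservative because the stage effect inflates the residual variance. Each arm adds 12 × 0.25 × 0.75 × d² = 2.25d² to the residual sum of squares, or 9d² over four arms. At d = 1.0 the variance is (44 + 9)/44 = 1.20 times too large.
- One cohort repeated: bias at most 0.09 SD, with no inflation.
- Dropped dose: bias 0.38-0.40 SD (d = 0.5) or 0.75-0.80 SD (d = 1.0), with false positives of about 15% or 26-30%. If its cohort had been repeated first, about 17% or 34%.
- Two doses dropped, retained dose: bias -0.15 SD at d = 1.0, false positives about 11%.

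**With stage as a factor.** Bias is 0 and the rate about 10% in every scenario. The SE of the contrast stays at 0.408 SD as planned, goes from 0.379 to 0.380 after cohort 1 is repeated, and from 0.645 to 0.707 for a dropped dose.

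**Adjusted dose.** Stage shares remain 3/12 in every arm, so g = 0. The group would hold 3 patients on the Stage 1 dose and 9 on the adjusted one.

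**The case against.** The strongest objection is that the planned design is balanced: 3 and 9 in every arm, so an additive stage difference cancels. That stands. A reader might infer that any use of Table 3, including a shorter window, makes dose-placebo differences reflect stage. The documents do not support this, since a shortened window, an adjusted dose or repetition of all cohorts leaves the shares equal. Nor does one repeated cohort matter much. It does open a gap of 0.40 - 0.25 = 0.15 between two doses, but that is not a placebo contrast.

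Pooling is inferred from the counts and not stated. Section 15 defers detail to a separate SAP that could add stage, and section 8.4.2 requires a safety report for each cohort. So it cannot be said that every result ignores stage. Even so, the groups and tests written here omit it, and the cohort reports serve escalation decisions.

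The study is an exploratory pilot, safety and clinical parameters are described, and explicit dose-placebo contrasts are named only for PD. A dropped dose contributes only 3 patients, or 6 if its cohort was repeated. This limits the stakes. Finally, whether placebo counts as a remaining dose level in Table 3 is unclear, so the 0.80 gap is conditional.

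**Conclusion.** The point holds for two adaptations. A dropped dose would be compared with a placebo group drawn mostly from the other stage, at a bias of 0.75-0.80 times the stage effect. An adjusted dose would share a label with a different dose, which is a labelling fault and not a stage bias against placebo. Elsewhere, omitting stage costs only some precision, and only if the stages differ.

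The rates rest on an assumed additive stage effect of 0.5 or 1.0 SD. Treatment-by-stage interaction and calendar drift across the sequential Stage 1 cohorts were not modelled. The latter does not fully cancel, because each dose's Stage 1 patients come from one cohort and the placebo patients from three.

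A reader might also infer that Stage 2 alone should be the lead comparison. The documents do not require that. It would raise the SE from √(2/12) = 0.408 to √(2/9) = 0.471 SD, although the pooled comparison is balanced as planned.

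**What to change.** In sections 15.1.1 and 15.1.5, and in the separate SAP for the post-hoc analysis in section 15.5:

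1. Include stage as a factor in the ANOVA and the PD contrasts, matching the two randomisation lists. Replace Mann-Whitney and Kruskal-Wallis with stage-stratified rank tests (van Elteren for two groups, its multi-group extension otherwise).
2. Define groups by planned dose, so that an adjusted Stage 2 dose is not merged with the Stage 1 dose of the same label.
3. Report a dropped dose descriptively beside Stage 1 placebo.
4. Optionally show a Stage 2-only table as supportive, without replacing the pooled, stage-adjusted comparison.

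The cost is about one degree of freedom of 44, a few sentences, and a wider SE for a dropped dose (0.645 to 0.707 SD), which reflects how little concurrent data it has.

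The history of changes and section 15.5 refer to an original analysis. If that is already complete, apply these rules to the post-hoc analysis and report them as a sensitivity analysis of the original results.

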15.1.2 Analysis Sets

Safety analyses will be conducted on the safety analysis set, including all patients who received at least one dose of the study drug.

Pharmacodynamic (PD) analyses will be conducted on the PD analysis set, including all patients who received at least one dose of study drug, had at least one post-baseline PD assessment and no protocol deviation with a major effect on PD results.

Pharmacokinetic (PK) analyses will be conducted on the PK analysis set, including all patients who received at least one dose of MOTREM, had at least one post-baseline PK assessment and no protocol deviation with a major effect on PK results.

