6.4.3 Benefit-Risk Assessment

The benefit risk ratio of the study design is considered favourable because (i) throughout the study, all patients receive standard therapy for the treatment of their septic shock, (ii) progression to next dose level/next stage only after evaluation of data from previous groups/cohorts and approval from an independent Data Safety Monitoring Board (DSMB) and (iii) patients with a deterioration of their disease will be withdrawn from the study.

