9.5 Withdrawal of Patients

The investigator will withdraw a patient from the study (i.e. from any further study medication or study procedure) for one or more of the following reasons:

- At the request of the patient or legal representative (withdrawal of consent)
- If, in the investigator's opinion, continuation of the study would be detrimental to the patient's well-being
- Use of/need for a prohibited medication which in the opinion of the Sponsor or Investigator may jeopardise the study results or represent a risk to the participant
- Major violation of the protocol
- Is withdrawn from the study upon the request of Sponsor, including if Sponsor terminates the study.

As far as possible, all examinations scheduled for the final study day (EOS) must be performed on all patients who receive the investigational product but do not complete the study according to the protocol. In any case, the respective case report form (CRF) section entitled "End of Study" as well as survival status at days 28 and 90 must be completed.

In all cases, the reason for and date of withdrawal must be recorded in the CRF and in the patient's medical records. The patient must be followed up to establish whether the reason was an AE, and, if so, this must be reported in accordance with the procedures in section 13 on page 42.

The investigator must make every effort to contact patients lost to follow-up. Attempts to contact such patients must be documented in the patient's records (e.g., times and dates of attempted telephone contact, receipt for sending a registered letter). At least two documented attempts to contact the patient must be made before a patient can be considered lost to follow-up.

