10.7.1 Allowed and Not-Allowed Medications and Procedures

All treatments and procedures required for the treatment of the patient's illness are permitted.

The following concomitant treatments are not permitted during the treatment phase of this study (i.e. study drug infusion):

- Bolus glucocorticoid treatment exceeding 300mg of hydrocortisone or equivalent per day for a maximum of three days

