15.1.5 Safety Analyses

Adverse events will be coded using the MedDRA dictionary version 18.1 or higher. Treatment emergent adverse events (events start after the first dose of investigational treatment or events present prior the administration of investigational treatment and worsened during the study (increased in severity)) will be classified by primary system organ class, preferred term and treatment group. Separate summaries will be performed for study medication related events, death, serious adverse events, adverse events leading to discontinuation of study medication and other adverse events of interest.

Other safety parameters that will be assessed include safety laboratory parameters (haematology, coagulation, biochemistry, arterial blood gases etc), vital signs (SBP, DBP, heart rate and body temperature), ECG and exposure of MOTREM. The parameters will be listed by treatment group (Placebo, Dose level 1, Dose level 2 and Dose level 3), patient and visit and summarised using standard descriptive statistics. All abnormal values will be identified in patient data listings. Changes from baseline will be described.

PD Analyses: Pharmacodynamic data will be listed by treatment, patient, and visit/time. Summary statistics will be provided by treatment and visit/time. Geometric means and CV will be presented for the primary and secondary PD endpoints.

PD endpoints will be compared between treatments with an ANOVA on logs. Each MOTREM dose group will be compared to placebo with a contract t-test at the 2-sided 10% level.

PK Analyses: Observed MOTREM serum concentrations will be summarised by treatment and corresponding time when sampling occurred. Derived PK parameters will be summarised by treatment.

Clinical Analyses: Several clinical parameters as the clinical events related to sepsis and its complications, the SOFA score total and each sub-score (respiratory, cardiovascular, hepatic, coagulation, renal and neurological system), the vasopressor use, the mechanical ventilation and intubation will be described by treatment group and visit. Standard descriptive statistics will be used.

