17.2 Clinical Database

Data Management will create the database under Oracle (V10.2.04 or higher) and the eCRF entry screens.

The eCRF application will be accessible by connecting on a dedicated and secure website using Clinsight Online module. Each user will connect by using personal identifier / password.

The Data Manager will write the Data Handling Manual (DHM) which describes the various data management steps, the database structure (name and format of the items) and the annotated eCRF, and the validation plan.

The investigator, sub-investigators or its designated representative will enter the data for each patient on online eCRF application. The data will be extracted from the ORACLE database and formatted as SAS files (V9.4).

The Data Manager will program the consistency checks defined in the validation plan. These checks will result in the production of Electronic Data Clarification Forms (eDCFs). The investigator or designated representative will directly answer to these eDCFs on the eCRF application.

Adverse events will be coded using MedDRA dictionary, and concomitant treatment will be coded using WHO-DRUG dictionary version 2015-3 or higher.

At the end of the validation process, the Data Manager will produce listings which describe all protocol deviations. The status of these deviations (minor or major) will be discussed during the pre-analysis review, and the analysis population will be defined.

At the end of the data management process, the database will be frozen and the SAS files will be sent to INOTREM SA according to the Data transfer process.

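### The PD analysis set drops dosed patients for deviations judged after randomisation, and no biomarker contrast on all dosed patients is planned beside it

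*Combined protocol and SAP*

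**What the plan says.** Section 15.1.2 defines three sets. The safety set is every patient who received study drug. The PD set adds that the patient "had at least one post-baseline PD assessment and no protocol deviation with a major effect on PD results". Section 15.1.5 compares PD endpoints by ANOVA on logs and adds: "Each MOTREM dose group will be compared to placebo with a contract t-test at the 2-sided 10% level" (contract is evidently a slip for contrast). No PD analysis of all dosed patients is described.

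No list of deviations with a major PD effect is given. Section 17.2 settles the matter late: "The status of these deviations (minor or major) will be discussed during the pre-analysis review, and the analysis population will be defined".

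Three other places link deviation or withdrawal to the course of the illness:
- Section 10.7.1 has one entry under treatments not permitted during infusion: "Bolus glucocorticoid treatment exceeding 300mg of hydrocortisone or equivalent per day for a maximum of three days".
- Section 9.5 gives as a withdrawal reason "Use of/need for a prohibited medication which in the opinion of the Sponsor or Investigator may jeopardise the study results".
- Section 6.4.3 states that "patients with a deterioration of their disease will be withdrawn from the study".

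Losses are not made good. Section 15.1.1 says: "Missing safety, pharmacodynamic, pharmacokinetic and clinical data will not be replaced and will be treated as missing from summary and statistical analyses". Section 9.5.1 allows no replacement in stage 2.

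**The concern.** Randomisation makes the arms comparable at the start of infusion. A filter applied afterwards keeps them comparable only if it is unrelated to outcome or acts alike in every arm. A deviation prompted by persisting shock is related to outcome. The cytokines in Table 2 are likely to be high in the same patients, and a drug that dampens inflammation could change how many of them deviate. The set could then lose more of its high-biomarker patients from placebo than from an effective dose, and the contrast would move toward no effect.

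The dose/PD relationship is a secondary objective (section 7), and section 6.3 says the data will inform the design of later studies. With 12 patients per group, one to three exclusions are enough to matter.

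**Working it through.** **Group size.** Section 15.2 says "the sample size 48 patients overall (N=12 for each dose level) was chosen". Each dose has 3 (stage 1) + 9 (stage 2) = 12 patients. Placebo has 3 × 1 + 9 = 12. The total is 4 × 12 = 48, which agrees. One, two or three exclusions from a group are 8%, 17% or 25%.

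**Selection model (assumed; the plan gives no PD effect size, SD or exclusion rate).** The log biomarker Y has SD 1, with mean 0 on placebo and −d on a dose, d = 0.5 or 0.8. The probability of exclusion is e(Y) = 1/(1 + exp(−a − bY)), with b the log odds ratio per SD and a set to give the placebo exclusion rate. The retained mean in an arm is E[Y(1 − e(Y))]/E[1 − e(Y)], found by numerical integration.

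Example with 17% excluded, odds ratio 3 and d = 0.8. The placebo mean moves from 0 to −0.157 and the dose mean from −0.8 to −0.884. The contrast is −0.884 + 0.157 = −0.727, and the shrinkage is 1 − 0.727/0.8 = 9%.

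Shrinkage over both values of d:

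| Placebo excluded | Odds ratio 1.5 | Odds ratio 3 | Odds ratio 5 |
|---|---|---|---|
| 8% | 1% | 5–6% | 8–9% |
| 17% | 2% | 9–10% | 14–15% |
| 25% | 3% | 12–13% | 18–20% |

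At 17% of placebo and odds ratio 3 to 5, 7% to 11% of the dose arm is excluded. If d = 0, the model excludes equally from both arms and the bias is zero.

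**Harsher model (assumed).** A simulation removed the most severe patients from placebo only, with severity correlated with the log biomarker (four-arm ANOVA, 12 per arm, two-sided 10%).
- Correlation 0.5, true effect −0.8 SD: removing 2 gives −0.66 SD and cuts power from 61% to 46%. Removing 3 gives −0.61 SD and 39%.
- No true effect, 3 removed, correlation 0.3 to 0.7: bias is 0.12 to 0.28 SD, and the false-positive rate rises from 10% to 11–16%.
- Two removed from every arm: bias is about zero.

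**Loss of numbers alone.** For a 1 SD effect, power is about Φ(1/√(1/n₁ + 1/n₂) − 1.645). At 12 v 12 this is Φ(2.449 − 1.645) = 78.9%. At 12 v 10 it is Φ(2.335 − 1.645) = 75.5%. Uneven selection matters more than the smaller sample.

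**What keeping these patients does.** Suppose the deviation is steroid use that lowers the biomarker by s. With proportions p (placebo) and q (dose) affected, the all-dosed contrast shrinks by s(p − q)/d. For p = 0.167, q = 0.085, s = 0.5 and d = 0.8, that is 0.5 × 0.082/0.8 = 5%. At 17% placebo use and odds ratio 3 to 5:
- s = 0.3 to 0.5: 3% to 7%
- s = 1.0: 10% to 14%

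The deviation-excluded set shrinks by 9% to 15% under the same conditions. With odds ratio 1.5 and s = 0.5, the all-dosed contrast shrinks slightly more than the excluded set (about 2.5% against 2%).

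**The case against.** **The glucocorticoid route is inferred.** No section calls it a deviation with a major PD effect. Section 10.7.1 bars only bolus use above its threshold during infusion, and otherwise permits all treatment that the illness requires. Mis-timed samples or dosing errors fit section 15.1.2 equally well and need not depend on outcome. This stands: neither the number of exclusions nor any imbalance can be derived from the documents.

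**Keeping steroid-exposed patients is not neutral.** A reader might infer that it only adds noise. The last calculation shows otherwise: it moves the contrast in the same direction, and for a large steroid effect by about as much. This also stands, and it is why both analyses should be reported.

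**The shift is small beside sampling error.** The largest case in the table, 18% of 0.8 SD, is about 0.15 SD. The standard error at 12 v 12 is √(2/12) = 0.41 SD. That is fair, and limits the weight of the point.

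**The review of deviations is probably blinded.** Section 8.4.1 keeps unblinded data from the study team until database lock, and section 17.2 places the review before the freeze. A reader might infer that exclusions could be chosen knowing the arm; the text does not support that. Blinding does not remove selection that runs through the patient's course, however.

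**The separate SAP may deal with it.** Section 15 refers to one, to be final before unblinding (section 15.4). It is not in the text available, and the protocol promises neither a pre-specified list nor an all-dosed PD contrast.

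**Conclusion.** The point holds as a conditional one. The PD set is filtered on events after dosing, the dose-placebo contrasts depend on it, and no all-dosed PD contrast is planned. Whether bias follows depends on who is excluded, which the documents do not determine. Under the assumed selection model, attenuation is about 5% to 20% for odds ratios of 3 to 5 with 8% to 25% of placebo excluded, 1% to 3% for an odds ratio of 1.5, and about zero when exclusions are equal and non-selective.

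Two stronger readings are not supported. The plan does not say that steroid-treated patients will be excluded. Nor does the filter hide harm in the main sense: safety is the primary endpoint and is analysed on all dosed patients. What is exposed is a set of exploratory biomarker contrasts in a pilot study without multiplicity adjustment. The change is still worth making, because it is cheap and those contrasts are meant to guide later studies.

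**What to change.** In section 15.1.2 and the SAP:

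1. Run the dose-placebo PD contrasts on all patients who received study drug and have at least one post-baseline PD sample, by assigned arm. Exclude individual samples only for technical reasons (mishandled, unassayable, wrong time).
2. Report the present deviation-excluded set beside it as a supportive analysis.
3. List the deviations that count as major for PD, and complete their classification, before the unblinding in section 15.4. Some biomarker results may still be outstanding then.
4. Tabulate exclusions by arm and reason.
5. State that the all-dosed contrast estimates the effect of assignment, including any steroid use, and can be attenuated by it.

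The cost is wording and one extra run of the PD tables. No treatment or withdrawal rule changes. The change does not recover patients without a post-baseline sample, or samples never taken after withdrawal under section 9.5.
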